3.3. Laboratory Procedures

3.3.1. Processing and Isolation of Tumor, Circulating Tumor Cells, Immune Cells and Progenitor Cells

Within 24-72 hours after blood draw or leukapheresis collection, the PBMC product obtained from peripheral whole blood and/or leukapheresis will be processed according to *BioCytics'* internal SOPs. Tumor cells, immune cells, and progenitor cells may be immuno-magnetically captured or flow sorted, also in accordance with *BioCytics'* SOPs. The isolated tumor cells (whether obtained from liquid biopsy measures or discarded tissue), immune cells, and progenitor cells may then be cultured, harvested, or cryopreserved. These cells may be stored in BioCytics' biobank or biorepository and sourced for research use only to external collaborators and/or vendors for research across all scientific fields and not limited to immunotherapy cancer research.

Version Date: 8-Dec-2020

3.3.2. Harvesting of Circulating Tumor Cells, Immune Cells and Progenitor Cells

Using standard cell culture techniques, tumor cells, immune cells and progenitor cells may be expanded according to *BioCytics'* internal SOPs.

3.3.3. Cryopreservation of Circulating Tumor Cells, Immune Cells and Progenitor Cells

Using standard cryopreservation techniques, tumor cells, immune cells and progenitor cells may be rate-controlled frozen, after appropriate selection, flow sorting or alternative approach, and possible expansion, enrichment and harvesting, in accordance to *BioCytics'* internal SOPs.

3.3.4. Storage of Plasma for Biomarker Discovery

Using standard centrifugation techniques, plasma may also be separated from whole blood or collected from the leukapheresis CMNC procedure and frozen according to *BioCytics'* internal SOPs for future biomarker discovery and biobanking/biorepository storage and sourcing.

4. ADVERSE EVENT REPORTING

Since this is an observational prospective biospecimen collection laboratory study, adverse events are not anticipated. Although not anticipated, any adverse event (AE) or serious adverse event (SAE) whether attributed or related to study procedures occurring in a patient after providing informed consent, will be documented in the study site(s)' electronic medical records (EMR), as well as tracked in *BioCytics*' data logs. AEs and SAEs are reviewed by the Principal Investigator, as well as by the Quality Systems Manager and QA study team members during the monthly QA meetings.

All SAEs and AEs will be assessed by the Principal Investigator or treating oncologist for severity, relationship to the investigational/study procedure(s) and whether the event meets criteria of an SAE. If criteria are met for a serious adverse event, whether attributable or related to study procedures, the SAE will be reported by the Principal Investigator to *BioCytics* immediately, and no later than 24 hours of learning of its occurrence. *BioCytics* may also contact the Principal Investigator to obtain further information on a reported Serious Adverse Event. *BioCytics* may also report the SAE to its respective Institutional Review Board immediately, and no later than 24 hours of learning of its occurrence and document all said communication/correspondence between all parties: investigator, sponsor, and IRB/IEC.

To date, *BioCytics* has observed one unexpected and unrelated death the day after a blood donation. Upon the Principal Investigator's knowledge of this event, the IRB was immediately notified, and documentation of this event was entered in the site's EMR. With respect to leukapheresis, to date there have been 135 leukapheresis collection procedures, out of which there have been only 14 mild reactions reported, constituting 10.37% of the total runs. These AE's were assessed by the clinical staff and most were due to transient mild symptoms of citrate related hypocalcemia, manifested as a mild peripheral sensory paresthesia (tingling) in toes and peri-orally, which resolved by giving an additional oral calcium carbonate (Tums) and reducing the pheresis flow rate. Other mild AE symptoms related to leukapheresis were mild chills (or

Version Date: 8-Dec-2020

Confidential 37 | Page

feeling cold) which resolved with a warming blanket and feeling symptoms of hunger (mild hypoglycemia) which resolved with a sports drink. Lastly, there have not been any clinically significant venipuncture related issues observed in the 587 patients that have been enrolled to date.

5. STATISTICAL METHODS

5.1. Sample Size Determination

An approximate of 1500 cancer patients and/or healthy volunteers are to be enrolled in this study. The sample size is not determined from a power analysis and may be incremented based on the Principal Investigator's discretion and upon IRB/IEC approval.

5.2. Statistical Consideration

The study is not powered for prospective statistical significance, however retrospective statistical tests may be applied to determine preliminary trends between tumor viability/apoptosis assays (TAVA), lymphocyte tumor cytotoxicity assay (LTCA), CTC enumeration, phenotyping, lymphocyte flow cytometry, and clinical tumor responses.

5.3. Statistical Analysis

All data will be listed individually by study subject. For quantitative parameters, summaries for descriptive statistics will include the mean, standard deviation, minimum, median, and maximum. For qualitative parameters, summaries for descriptive statistics will include the frequency and percentage.

6. VALIDATION OF TUMOR APOPTOSIS-VIABILITY ASSAY (TAVA) AND LYMPHOCYTE TUMOR CYTOTOXICITY ASSAYS (LTCA)

Validation of *BioCytics'* TAVA and (LTCA) will be compared to other tumor profiling assays that may have already been performed as clinical standard of care (such as Foundation One, Caris, ImmunoSeq).

Apoptosis is characterized by loss of membrane integrity and the appearance of "membrane blebs" due to the ballooning appearance of the cell membrane. These morphological changes can be monitored using time-lapse video microscopy. As an alternative validation approach, we will confirm our TAVA & LTCA results by examining morphological features of apoptosis.

Results from the TAVA & LTCA may be reported to the treating oncologist for research purposes only. These research results will not affect or change standard of care or treating regimens established by the National Comprehensive Cancer Network (NCCN) guidelines.

Version Date: 8-Dec-2020

Confidential 38 | Page

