2.2 Endpoints

2.2.1 Primary Endpoint

Successful selection of PD-1⁺ and CTLA4⁺ T cell, and other immune cellular fractions from peripheral blood or leukapheresis of study subjects by using antibody conjugation, and evaluation of functional *ex vivo* anti-tumor cytotoxicity against targeted autologous tumor cells.

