presence of a parent or legal guardian. These include nasal, NP, and/or OP swabs, saliva and/or urine collections, and microcapillary sampling. Additionally, no viral serology will be obtained in these subjects as they require a peripheral whole blood draw, which is outside the scope of pediatric participation.

Screening Visit

The screening visit may occur at any time and regardless of other concomitant treatment regimens.

Cancer Cohort Screening Visit Includes:

- Introduction of BioCytics 0001
- Eligibility review
- Informed consent and signature
- Enrollment and assignment to subject ID number
- Screening baseline reference labs: CBC, CMP, urine pregnancy test (if woman of childbearing potential), and viral serology for HIV, hepatitis B surface antigen, and hepatitis C positive RNA with reflex PCR
- ECOG Performance Status determination
- Prior and concomitant anti-cancer treatment documentation
- Tumor pathology report documentation
- Tumor Status (NED, PD, SD, PR, CR) as determined by the treating oncologist
- Tumor markers may be drawn as deemed appropriate by treating oncologist (i.e., CEA, CA19-9, PSA, CA27-29, CA-15-3, CA 125)
- If applicable, additional biospecimen collection may be obtained at screening (i.e., peripheral whole blood, microcapillary sampling, discarded fluid, saliva, urine, and/or stool collection)
- Possible 5-20 minutes of light to moderate exercise prior to whole blood draw(s)

Healthy Volunteer Cohort Screening Visit Includes:

- Introduction of BioCytics 0001
- Eligibility review
- Informed consent and signature
- Enrollment and assignment to subject ID number
- Viral serology for HIV, hepatitis B surface antigen, and hepatitis C positive RNA with reflex PCR for all adult healthy volunteers, excluding convalescing COVID-19 healthy volunteers and healthy volunteers who are current employees of *BioCytics'* and/or the study site(s)' who choose not to participate in leukapheresis collection
- Screening baseline reference labs of CBC, CMP, and urine pregnancy test (if woman of childbearing potential) are only required for adult healthy volunteers who are potential

Version Date: 8-Dec-2020

Confidential 25 | Page

leukapheresis candidates or who have a history of autoimmune disease or inflammatory disorder

- If applicable, additional biospecimen collection may be obtained at screening (i.e., peripheral blood, microcapillary sampling, nasal, NP and OP swabbing, saliva, urine, and stool collection)

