- Possible 5-20 minutes of light to moderate exercise prior to whole blood draw(s)
- For pediatric subjects (5-17 years of age), biospecimen(s) collection(s) limited to minimally invasive procedures: swabbing (nasal, NP and/or OP), microcapillary sampling, saliva and/or urine collection

Study Visit(s):

For the cancer cohort, each study visit will mostly occur at a patient's next scheduled treatment or follow-up visit; however, study visits may be scheduled specifically for biospecimen collection or leukapheresis collection that fall outside of their routine scheduled visits. Leukapheresis collection visits will occur no more frequently than every 4 weeks, and will not occur while a patient is actively on an investigational therapeutic clinical trial. Biospecimen collection visits may occur more frequently as long as deemed appropriate by the principal investigator or treating oncologist's discretion.

For the healthy volunteer cohort, visits may occur no more frequently than every 4 weeks for leukapheresis collection. Biospecimen collection visits may occur more frequently as long as deemed appropriate by the principal investigator or treating physician's discretion.

Cancer Cohort Study Visit(s) Includes:

- ECOG Performance Status determination
- Adjuvant treatment documentation
- Tumor status (NED, PD, SD, PR, CR) as deemed necessary by the treating oncologist
- Tumor markers may be drawn as deemed appropriate by treating oncologist (i.e., CEA, CA19-9, PSA, CA27-29, CA-15-3, CA 125)
- If applicable, additional biospecimen collection may be obtained at screening (i.e., peripheral whole blood, microcapillary sampling, discarded fluid, saliva, urine, and/or stool collection)
- Possible 5-20 minutes of light to moderate exercise prior to peripheral whole blood draw or leukapheresis collection
- If leukapheresis collection visit, CBC, CMP, and urine pregnancy test (if women of child-bearing potential), will be performed prior to the leukapheresis procedure taking place, as an additional safety measure.

Healthy Volunteer Cohort Study Visit(s) Includes:

 Treatment documentation if healthy volunteer has a clinically significant condition, such as an autoimmune disease or inflammatory disorder

Version Date: 8-Dec-2020

Confidential 26 | Page

- Additional biospecimen(s) collection(s) including peripheral whole blood, microcapillary sampling, saliva, urine, and/or stool collection, and nasal, NP and/or OP swabbing (if COVID-19 subject)

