3.2.4. Tumor Status

Tumor status, as defined by the Response Evaluation Criteria in Solid Tumors (RECIST), will be documented by the treating oncologist.

Tumor status may be classified as: No Evidence of Disease (NED), Progressive Disease (PD), Stable Disease (SD), Partial Response (PR), or Complete Response (CR). For adjuvant stage I, II, & III cancer patients in "remission", prognostic risk factors that predict relapse may also be tracked (based on their stage prognosis). Tumor status will be obtained from the treating oncologist, if deemed appropriate, at each study visit.

Tumor markers (CEA, CA19-9, PSA, CA27-29, CA15-3, CA-125, and/or circulating tumor DNA (ctDNA) or urinary tumor DNA (utDNA) may be drawn at baseline and monthly, according to standard of care and as deemed appropriate/necessary by the treating oncologist.

Tumor status and tumor markers will assist in correlation of viability-sensitivity assays, and correlation of circulating tumor cell enumeration with clinical response.

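### Section 6 lets TAVA and LTCA results reach the treating oncologist with no timing condition, although that role also grades tumor status, so the exploratory TAVA-response correlation is open to unblinded-assessor bias

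*Protocol*

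**What the plan says.** **Release of results.** Section 6 states "Results from the TAVA & LTCA may be reported to the treating oncologist for research purposes only". It adds that "These research results will not affect or change standard of care or treating regimens" set by national guidelines. It does not say when a result may be released relative to any clinical assessment.

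**Who grades response.** The screening list in section 3.2.1 has "Tumor Status (NED, PD, SD, PR, CR) as determined by the treating oncologist". The list for later visits has "Tumor status (NED, PD, SD, PR, CR) as deemed necessary by the treating oncologist". Section 3.2.4 defines status by RECIST, has the treating oncologist document it, and adds "Tumor status will be obtained from the treating oncologist, if deemed appropriate, at each study visit". Footnote 4 of Appendix 1 likewise confines later grading to occasions when standard care or treatment calls for it. No independent or masked read is named.

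**How status is used.** Section 3.2.4 says "Tumor status and tumor markers will assist in correlation of viability-sensitivity assays, and correlation of circulating tumor cell enumeration with clinical response". Section 5.2 says "retrospective statistical tests may be applied to determine preliminary trends between tumor viability/apoptosis assays (TAVA", and its list goes on to LTCA, CTC enumeration and other laboratory measures, and clinical tumor responses. The same section says that the study is not powered for prospective significance.

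**The concern.** When the person who grades an outcome may already know the measurement to be correlated with it, the two are no longer recorded independently. A borderline call between stable disease and partial response, for example, may drift toward what the assay suggested. Grading after screening is also discretionary, so a known result could influence whether and when status is recorded as well as the grade. Either route can create or inflate an apparent trend between TAVA and response.

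The stakes are modest but not nil. Section 1.9 names correlation with clinical response among the steps that may enable diagnostic TAVA reports, and section 2 says that data are being collected for a future device submission. A trend that cannot be separated from knowledge of the assay result would be weak support for either. Sections 7.4 and 7.5 disclose that the Principal Investigator is also a treating oncologist and the sponsor's chief executive. Formal reporting is therefore not the only way in which a grader might learn a result.

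**Working it through.** The protocol states no figure on this point, so there is none to reproduce. The check is a side-by-side reading.

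1. *May the grader receive the assay result?* Yes. Section 6 permits it for the treating oncologist, without a time or condition.
2. *Is it the same role?* Yes. Sections 3.2.1 and 3.2.4 name the treating oncologist as the source of tumor status at screening and later.
3. *Are the two then related?* Yes. Section 3.2.4 does so in firm terms for viability-sensitivity assays. Section 5.2 does so optionally for TAVA and LTCA. LTCA therefore meets clinical response only through the optional tests.
4. *Does any rule keep them apart?* None was found: no masking, no independent review, no locking of status before release, and no record of the release date. Section 8.4 tracks processing, storage and distribution of the sample, and links results to specimens. It does not name the date on which a result reached the oncologist.
5. *Do the stated limits close the gap?* The research-use restriction governs what a result is for, and the second limit governs treatment. Neither stops a grader from knowing the result when assigning a status.
6. *What depends on the correlation?* No endpoint does. The primary endpoint concerns selecting PD-1 and CTLA4 T cells and "other immune cellular fractions from peripheral blood or leukapheresis of study subjects by using antibody conjugation", with ex vivo cytotoxicity. The secondary endpoint compares selected with unselected cells. The section 6 validation comparisons, with other profiling assays and with cell morphology, do not use tumor status. Tumor markers, the other input in section 3.2.4, are laboratory values and are not graded.

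**Illustration of the mechanism only.** Every input here is an assumption. Suppose a binary TAVA call (the protocol defines none) on a drug the patient is receiving, and no true association. Let p be the true response rate, b the borderline share of status calls, q the share of borderline calls that follow a seen result, and r the share of results released before grading. With s = b × q × r, observed response is p(1 − s) + s when the assay reads sensitive and p(1 − s) when it reads resistant.

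| p | b | q | r | s | Sensitive | Resistant | Odds ratio |
|---|---|---|---|---|---|---|---|
| 0.30 | 0.20 | 0.50 | 0 | 0 | 30.0% | 30.0% | 1.00 |
| 0.30 | 0.20 | 0.50 | 0.10 | 0.01 | 30.7% | 29.7% | 1.05 |
| 0.30 | 0.20 | 0.50 | 0.50 | 0.05 | 33.5% | 28.5% | 1.26 |
| 0.30 | 0.20 | 0.50 | 1 | 0.10 | 37.0% | 27.0% | 1.59 |
| 0.30 | 0.10 | 0.25 | 0.50 | 0.0125 | 30.9% | 29.6% | 1.06 |

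For the third row, (0.335/0.665)/(0.285/0.715) = 0.504/0.399 = 1.26. The table shows that the bias vanishes when nothing is released before grading and otherwise depends on inputs that nobody has. It is not evidence of how large the bias would be in this study.

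**The case against.** The strongest reply is that the protocol is silent here rather than wrong. The sections do not contradict each other, release is optional, the tests are optional and unpowered, and flagging pairs for a sensitivity analysis is ordinary material for a statistical analysis plan, which is not shown. Much of this stands, and it is why the point is minor. What remains is that the order in which a grader learns a result and records a status is study conduct. The protocol sets that conduct in sections 3.2.4 and 6, and an analysis plan can separate exposed pairs only if exposure was recorded.

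A second reply is that RECIST and the research-use restriction already protect grading. They help: published criteria narrow discretion, and a research-only result is arguably not meant to inform a clinical determination. Neither is masking.

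Third, LTCA tests the patient's lymphocytes ex vivo, and human application is left to a later protocol. It does not directly predict response to current therapy, so the direction of any drift is unclear. This stands, and the case for LTCA is correspondingly weaker.

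A reader might also infer that exposed pairs could never be identified afterwards. The documents do not show that. Sections 8.4 and 9.3 link results to specimens and retain laboratory records, so some release dates might be reconstructed. The narrower statement is that no section requires the date to be kept.

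**Conclusion.** The point holds as a low-cost, optional improvement. The protocol permits assay results to reach the person who grades tumor status, provides no masking or ordering, and plans to relate the two. The exploratory TAVA-response correlation is therefore open to unblinded-assessor bias.

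The size is unknown. It depends on how often results are released or seen before grading, how many status calls are borderline, and how far graders follow what they have seen. The protocol gives none of these.

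Stronger readings are tempting and should be resisted. The text does not show that bias will occur, since release is optional. It does not put the endpoints or the assay validation at risk, since neither uses tumor response. The disclosed interests of the Principal Investigator do not suggest misgrading. They are a reason to document the order of events and to count access through the sponsor role as well as formal release.

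**What to change.** Add three provisions to section 6:

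1. For every TAVA and LTCA result, record the date on which it is released to, or first seen by, the treating oncologist. This includes an investigator who has access through the sponsor.
2. Where practicable, release a result only after the first tumor status following collection of that specimen has been recorded.
3. Flag any tumor status graded after release or access. Report the correlation on all data, then repeat it without the flagged pairs. No data are discarded.

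The first and third provisions are the sturdier part. Because status after screening is graded only when judged appropriate, a strict hold could delay release for a long time or indefinitely, hence the wording on practicability. A hold also protects only the first status after collection, whereas the date allows any later status to be classified in the same way. A hold on formal release would not mask an investigator who can see results through the sponsor, which is why first sight is logged too.

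The cost is a few sentences and one date field, which can be kept against the study or product number already used under section 8.4. No visit, reader or procedure is added. The downside is that the oncologist sometimes sees a research-only result later.

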7. ETHICAL ASPECTS

7.1. Compliance

7.1.1. Good Clinical Practice

This study must be carried out in compliance with the protocol and in accordance with *BioCytics'* internal SOP. These are designed to ensure adherence to Good Clinical Practice, as described in the following documents:

- i) ICH (International Conference for Harmonization) Harmonized Tripartite Guidelines for Good Clinical Practice 1996; E6(R2) Good Clinical Practice: Integrated Addendum to ICH E6(R1) March 2018
- ii) Directive 91/507/EEC, The Rules Governing Medicinal Products in the European Community
- iii) Declaration of Helsinki, concerning medical research in humans

The Investigator agrees, when signing the protocol, to adhere to the instructions and procedures described in it and thereby to adhere to the principles of Good Clinical Practice to which it conforms. A copy of the Declaration of Helsinki is located on the internet at: http://www.wma.net.

7.1.2. Good Laboratory Practices (GLP) and Good Tissue Practices (GTP)

The trial will follow GLP and GTP requirements (see 21 Code of Federal Regulations Part 58 (GLP) and Part 1271 (GTP). Efforts are currently being made for the adherence of Good Manufacturing Processes (GMP) for future IND submission of immune-cell therapy autologous investigational product, as well as for future biobanking and sourcing of cells or cell products for clinical use.

7.2. Institutional Review Board/Independent Ethics Committee

Before implementing this study, the protocol, the proposed Informed Consent Form/HIPAA authorization, and other information to study subjects must be reviewed by an Independent Institutional Review Board/Independent Ethics Committee (IRB/IEC) per GCP guidelines. A signed and dated statement that the protocol and informed consent form have been approved by the IRB/IEC must be given to *BioCytics* before study initiation. The IRB/IEC will be notified for any and all amendments to this protocol, including administrative changes and those that change the study design. These changes in turn need approval by the IRB/IEC prior to implementation at the study site(s). Annual review of this protocol will be submitted to the IRB for continued approval or at a frequency deemed necessary by the IRB, regardless of a Change in Research (CIR) submission. In addition, the Principal Investigator will be required to submit, maintain, and archive essential study documents according to ICH GCP guidelines.

